6.2 Detailed Study Procedures

6.2.1 Recruitment and Informed Consent Process

Interested patients will be scheduled to meet with a qualified investigative staff member and receive an explanation of the study purpose and requirements in lay language. If interested in participating, patients will be given an IRB/IEC-approved study-specific informed consent form (ICF) to read and ask questions and share with family members if requested. Prior to a patient's participation in the study, written informed consent will be obtained in accordance with ICH GCP. The written IRB/IEC-approved ICF will be signed and dated by the patient and by the person who conducted the informed consent discussion. In addition, a statement to document the informed consenting process will be recorded in the patient's source documents.

Any patient who has difficulty understanding the ICF will discuss it with a research staff member. Research staff will work closely with patients in an effort to help them understand the requirements of their participation. Patients' questions must be answered fully by trained and qualified staff. Any patient who is unable to demonstrate understanding of the information contained in the ICF will be excluded from study participation.

The ICF and any other information provided to patients will be revised whenever important new information becomes available that is relevant to a patient's consent and continued participation in the study. The revised ICF and information must receive IRB/IEC approval/favorable opinion prior to use, and a copy of the IRB/IEC's approval/favorable opinion will be provided to the Sponsor/Sponsor's designee. The investigator, or a person designated by the investigator, will fully inform all patients of all pertinent aspects of the study and any new information relevant to the patients' willingness to continue participation in the study. This communication with the patient should be documented by the patient signing and dating the revised ICF and by written

documentation of this discussion with the patient in the subject's source documents available to Sponsor/Sponsor's designee or regulatory authorities for onsite review.

Patients who consent to participate in the study will receive a copy of the signed ICF and any other information provided to patients prior to the participation in the study. The original signed forms will be maintained at the investigator's site.

After providing and documenting consent on the IRB/IEC-approved written ICF, patients will be assigned their patient screening number and proceed to the Screening Period.

6.2.2 Visit 1 (Week -6 to -1) Screening Period

The following assessments will be obtained during the Screening Period and used to determine whether a patient meets eligibility criteria for the study. Patients meeting eligibility criteria at Screening must also meet eligibility criteria at the Baseline Visit. Patients meeting eligibility criteria at Screening must also meet eligibility criteria at the Baseline Visit including the completion of a valid 3 day Baseline PD diary. The PD diary training and evaluation instructions are described in [Section 7.1](#) and [Appendix 15.13](#).

Note: Confirm the arrangement for laboratory sample pick-up on the day of the Screening Visit with the courier (see Central Laboratory Procedures Manual).

6.2.2.1 Screening Assessments

1. Obtain written informed consent (see [Section 6.2.1](#)), and provide a copy to the patient.
2. Obtain demographics and previous medical history, including any co-existing pretreatment AEs.
3. Obtain neurological and PD history.
4. Obtain complete medication history including anti-PD medications (current and prior history). Record the date and approximate time of the most recent dose of levodopa taken prior to the Screening assessment.
5. Perform physical and neurological examination.
6. Obtain weight, height and calculate BMI.
7. Obtain and record serial BP and pulse measurements after at least 5 minutes supine rest and again after standing for approximately 1 and 3 minutes. Repeat these BP and pulse measurements 2 more times approximately 10 minutes apart.
8. Obtain 12-lead ECG. Ensure the ECG is collected when the patient is not experiencing dyskinesia that would interfere with an adequate recording.
9. Perform the following assessments in the ON state:
 - a. Perform full UPDRS Parts I, II, III (motor) and IV. UPDRS Part III should be performed approximately 1 to 3 hours after the patient has taken a scheduled dose of levodopa (preferably their morning dose of levodopa). UPDRS in the ON state will be measured at a time representative of the ON state in that patient, not in "best" ON.

- b. Modified Hoehn and Yahr stage in the ON state (estimate OFF state per history and document for entry criteria).
 - c. Administer the following assessment:
 - MMSE-II. (If the MMSE-II is not validated in the requisite language, the MMSE [Original] may be used.)
10. Administer the following assessments (may be done anytime during visit):
- a. C-SSRS.
 - b. Assessment for episodes of sudden onset of sleep.
 - c. mMIDI (Note: After Baseline, if patient has one or more positive modules on the mMIDI, their continued participation in the study should be discussed with the Medical Monitor).
11. For all applicable patients: Document method of contraception.
12. Obtain samples for the following laboratory tests and record the date and time of collection:
- a. For females who are postmenopausal for less than 2 years and who are not surgically sterile: obtain a blood sample for FSH.
 - b. For females of childbearing potential: urine pregnancy test.
 - c. Hematology and chemistry (including liver function tests).
 - d. TSH, free T3, free T4, and thyroperoxidase antibody.
 - e. Urine sample for urinalysis.
13. Instruct the patient (and any caregiver that will assist the patient to complete PD diaries during the study) on how to complete the PD diary, including the definitions of ON and OFF.
- a. Have patient (and caregiver, as applicable) review the PD diary training video.
 - b. Perform patient (and caregiver, as applicable) PD diary training.
 - c. Review the definitions of ON and OFF, including ON time according to categories “without dyskinesia”, “with non-troublesome dyskinesia” or “with troublesome dyskinesia”. Emphasize the need for the patient to be consistent in their use of the definitions when rating their status in the PD diary during the study.
 - d. When instructions appear to have been understood by the patient (and caregiver, as applicable), initiate a diary concordance session during which the patient and the diary trainer/rater concurrently complete separate training diaries during at least 5 consecutive half-hour intervals (minimum 2.5 hours).
 - During the diary concordance session, the patient must experience both ON and OFF. The 2.5 hour session may be extended, as needed, so that the patient experiences OFF. If the patient is OFF at the beginning of the session, they may be administered their next dose of levodopa-containing medication in order to experience ON.
 - During this time, other study-related assessments that do not interfere with the half-hourly ratings may take place.

14. When the diary concordance session is completed, the diary trainer/rater will review and assess diary concordance between the patient and the trainer/rater.
 - For the session, the patient is required to reach at least 80% overall diary concordance with the trainer/rater including at least 1 OFF interval.
 - If the concordance criteria are not achieved, the trainer/rater will schedule a second PD diary training and diary concordance session within the 6-week Screening Period, unless the patient declines further participation.
15. If the patient does not otherwise meet inclusion and exclusion criteria, e.g., if a laboratory result disqualifies the patient from participating in the study, the patient is considered a screen failure. Record the primary reason for screen failure in the source documents, appropriate eCRF module and all applicable eCRFs for a screen failure. For patients who remain eligible, proceed with instructions in [Section 6.2.2.2](#).
16. If the investigator determines the patient meets the inclusion and exclusion criteria:
 - a. Schedule the Baseline visit to occur within 6 weeks from the date of the Screening Visit and at a time approximately 1 to 3 hours after the patient has taken a scheduled dose of levodopa (preferably their morning dose of levodopa) to ensure the UPDRS can be collected in the ON state.
 - b. Instruct the patient to bring their medications (including anti-PD medications) to the Baseline visit so that they are able to maintain their regular treatment schedule.

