2.1.2 Secondary Objectives

The secondary objectives of this study are to evaluate the effects of tozadenant on the occurrence of daytime drowsiness, impulsive behavior, and suicidality.

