3.1.1 Study Duration Per Patient

Each patient will participate for up to 62 weeks, which includes a Screening Period of 1 to ≤ 6 weeks, followed by a Baseline Visit, 52 weeks of open-label treatment, and a Safety Follow-Up Visit 4 weeks after completion of investigational treatment:

- Screening Period: 1 to ≤ 6 weeks.
- Open-Label Treatment Period: 52 weeks.
- Post-Treatment Safety Follow-Up: 4 weeks.

The total anticipated study duration for an individual patient will be a minimum of 57 weeks and a maximum of 62 weeks. The end of the study is defined as the date of the last visit of the last patient in the study.

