6.2.3.2 Perform Baseline Assessments

Note: Confirm the arrangement for laboratory sample pick-up on the day of the Baseline Visit with the courier (see Central Laboratory Procedures Manual).

1. For all applicable patients: Determine contraceptive method used by patient and document.
2. Obtain samples for the following laboratory tests and record the date and time of collection:
 - a. For females of childbearing potential: urine pregnancy test.
 - b. Hematology and chemistry (including liver function tests).
 - c. TSH, free T3, and free T4.
 - d. Urine sample for urinalysis.

3. Obtain and record serial BP and pulse measurements after at least 5 minutes supine rest and again after standing for approximately 1 and 3 minutes. Repeat these BP and pulse measurements 2 more times approximately 10 minutes apart.
4. Obtain three 12-lead ECGs (3 serial readings, performed several minutes apart). Ensure the ECGs are collected when the patient is not experiencing dyskinesia that would interfere with an adequate recording.
5. Record the date and approximate time of the most recent dose of levodopa taken prior to UPDRS assessment.
6. Perform the following assessments in the ON state:
 - a. Perform full UPDRS Parts I, II, III (motor) and IV. UPDRS Part III should be performed approximately 1 to 3 hours after the patient has taken a scheduled dose of levodopa (preferably their morning dose of levodopa). UPDRS in the ON state will be measured at a time representative of the ON state in that patient, not in “best” ON.
 - b. Administer the following assessments:
 - PDQ-39.
 - EQ-5D-5L.
 - Non-motor Symptom Assessment Scale.
 - c. Have the patient complete the following self-assessment questionnaires:
 - ESS.
7. Administer the following assessments (may be done anytime during visit):
 - a. C-SSRS.
 - b. Fall questionnaire.
 - c. Assessment for episodes of sudden onset of sleep.
8. If the patient does not meet the criteria for study participation, the patient is considered a screen failure. Record the primary reason for screen failure in the source documents and appropriate eCRF module.

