6.2.3.4 Assignment and Dispensing of Investigational Medicinal Product

Note: Sites participating in Expanded PK Sampling should refer to [Appendix 15.9.1](#) for Assignment and Dispensing of IMP instructions.

1. For patients meeting all entry criteria, complete the IMP assignment transaction using the IXRS by following the procedures provided.
 - a. Dispense the open-label IMP bottle(s) assigned by the IXRS to the patient for this study visit. Each bottle consists of either 50 tablets of 120 mg tozadenant or 100 tablets of 60 mg tozadenant.
 - b. Record the date IMP was dispensed in IMP dispensing records including patient number, assigned IMP bottle number(s), and date and time IMP was dispensed.
 - c. Review the dosing instructions for the IMP with the patient, answer any questions, and remind the patient to return the IMP (including all used, unused and partially used bottles) at the next visit.
 - d. Patients will be instructed to take either two (2) 60 mg tablets or one (1) 120 mg tablet of the dispensed IMP by mouth BID, in the morning and in the evening preferably at the same time each day, for a total of either two (2) 120 mg tablets or four (4) 60 mg tablets per day. The evening dose should be approximately 12 hours after the morning dose. Patients will be instructed to take their morning and evening doses 1 hour before or 2 hours after a meal and to refrain from eating for 1 hour after dosing. Patients should take the first dose of IMP at home after the Baseline Visit.
2. Instruct the patient to take the first dose of IMP at home on the evening of dispensation.
3. Ensure that the patient understood the dosing instructions and the use of the extra doses included in the bottle if visit delayed and/or use of visit window.
4. Schedule the Week 2 visit. If needed, use the visit window in relation to the date of the Baseline visit.

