9.8.7. Modified Minnesota Impulsive Disorders Interview

mMIDI is reported at Weeks 2, 6, 12, 24, 36, 52, early termination and safety follow-up. For the mMIDI module scores and total score, if a question is not answered with a module, then that given module score and the total score will not be determined for the subject at the visit.

The mMIDI modules are Buying Disorder, Compulsive Gambling, Compulsive Sexual Behavior, Compulsive Eating, and Punding Behavior. The number and percent of subjects in each module with a positive/negative indication for the module will be reported. In addition, shift from baseline to each scheduled visit will be summarized.

All mMIDI data collected will be included in the data listings.

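### The mMIDI is not given at the predose Baseline Visit, so modules that turn positive between Screening and first dose can be tabulated as shifts on tozadenant: a cheap improvement

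*Protocol*

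**What the plan says.** Protocol 2.1.2 sets out to "evaluate the effects of tozadenant on the occurrence of daytime drowsiness, impulsive behavior, and suicidality". The mMIDI is the instrument for impulsive behavior.

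- **Screening.** Protocol 6.2.2.1, item 10, lists "c. mMIDI (Note: After Baseline, if patient has one or more positive modules on the mMIDI".
- **Baseline, before dosing.** Protocol 6.2.3.2, item 7, opens with "Administer the following assessments (may be done anytime during visit" and names three: the C-SSRS, the fall questionnaire and, last, "c. Assessment for episodes of sudden onset of sleep". The mMIDI is not among them. The Baseline cell of its row is blank in Protocol Table 1, Protocol Table 4 and SAP Table 1.
- **Next mMIDI.** Week 2 (Protocol 6.2.4, item 9; Appendix 15.9.2 for the expanded PK sites). Unscheduled visits are defined only from Baseline onward (6.2.21), so none is provided for in the gap.
- **Timing.** Protocol 3.1.1 gives "Screening Period: 1 to ≤ 6 weeks". Section 6.2.3.4 tells the site: "Instruct the patient to take the first dose of IMP at home on the evening of dispensation".
- **Analysis.** SAP 5.7 takes the last value before first dose as baseline and falls back on the Screening value when there is none on Day 1. SAP 9.8.7 counts positive and negative modules and adds that a "shift from baseline to each scheduled visit will be summarized".

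**The concern.** For the mMIDI, the fallback in SAP 5.7 is not an exception for missing data. It is the rule for every patient who follows the schedule. The baseline is then as old as the screening period, and SAP 9.8.7 has no provision for onset between Screening and first dose.

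The study has one arm. No control group shows how many modules would turn positive without the drug, so the before-and-after comparison has to do that work. The measures for the other two secondary effects (ESS and sudden onset of sleep for drowsiness, C-SSRS for suicidality) are all taken at Baseline before dosing.

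The form cannot repair the gap afterwards. The mMIDI in Appendix 15.4 has neither an onset date nor a recall window running from the previous visit. The sudden-sleep form in Appendix 15.3 does ask about the time since the last visit. A module first positive at Week 2 therefore cannot be dated from the mMIDI to before or after the first dose.

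**Working it through.** **Inputs.** Screening length s = 1 to 6 weeks (Protocol 3.1.1). First dose on the evening of the Baseline Visit (6.2.3.4). mMIDI visits at w = 2, 6, 12, 24, 36 and 52 weeks after Baseline (SAP 9.8.7). Week 2 window ±3 days (Table 1). Planned enrollment 450 (Protocol 11.9).

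**The plan's own figure.** Protocol 3.1.1 states a duration of 57 to 62 weeks per patient: 1 + 52 + 4 = 57 and 6 + 52 + 4 = 62. Both agree, so the range for s is the one the plan uses.

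**Age of the mMIDI baseline at first dose.** It equals s: 7 to 42 days.

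**Untreated share of the interval behind a shift.** Share = s / (s + w):

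| Visit | s = 1 week | s = 6 weeks |
|---|---|---|
| Week 2 | 1/3 = 33% | 6/8 = 75% |
| Week 6 | 1/7 = 14% | 6/12 = 50% |
| Week 12 | 1/13 = 8% | 6/18 = 33% |
| Week 24 | 1/25 = 4% | 6/30 = 20% |
| Week 36 | 1/37 = 3% | 6/42 = 14% |
| Week 52 | 1/53 = 2% | 6/58 = 10% |

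With the ±3-day window, the Week 2 range runs from 7/(7 + 17) = 29% to 42/(42 + 11) = 79%.

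**How many patients (illustration only).** The documents give no background rate. Assume a constant rate r of 1% to 10% new positive modules per patient-year and put all 450 patients at the same screening length. The expected number of predose onsets is 450 × (1 − exp(−r × days/365.25)):

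- 1-week screening (7 days): 0.1 to 0.9.
- 6-week screening (42 days): 0.5 to 5.1.
- For comparison, the first 14 days on drug at the same rates: 0.2 to 1.7.

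**With an mMIDI at Visit 2.** The baseline is 0 days old at first dose, and the untreated share at Week 2 is 0/(0 + 2) = 0%.

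**The case against.** The schedule looks deliberate. Exclusion 19 places the structured interview that follows a positive mMIDI within Screening, and footnote j and Appendix 15.4 agree. Exclusion 18, by contrast, names both Screening and Baseline for the C-SSRS. Other measures also rest on a Screening-only baseline, weight among them, and SAP 5.7 provides for that. This stands as an account of why the tables agree with one another. It does not remove the effect on the shift table.

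Other routes can catch predose onset. Adverse events are recorded from consent (Protocol 9.1.1), and history and pretreatment events since Screening are reviewed at Baseline (6.2.3.3). An overt disorder could be recorded there. So a reader who concludes that a predose mMIDI is the only means of telling the two apart goes too far. But these routes rely on open reporting, and neither changes the mMIDI table.

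A reader might also infer that eligibility is breached, since Section 6.2.2 says "Patients meeting eligibility criteria at Screening must also meet eligibility criteria at the Baseline Visit". The documents do not support that. The sentence requires eligibility still to hold, not that every instrument be repeated, and the MMSE-II and Hoehn and Yahr staging are Screening-only too.

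The shares assume a constant rate, which is doubtful. Anti-PD medication must be stable for 4 weeks before Screening and is checked for disqualifying changes at Baseline, but may be adjusted freely on treatment. Some mMIDI items ask about lifetime experience, so a new positive need not mark onset in the interval. Both points stand.

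Finally, the analysis is descriptive, so no test or sample size is affected. SAP 9.1 also counts patients who stopped because of program termination, so a further protocol amendment may be moot. The reporting change in the SAP would still be possible.

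**Conclusion.** The point holds as a cheap improvement. The mMIDI baseline is 1 to 6 weeks old at first dose for patients on schedule. A module that turns positive in that gap and remains positive at a later visit enters SAP 9.8.7 as a shift on tozadenant. The effect is largest at Week 2 and small by Week 52.

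Two stronger readings should be avoided:

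- That impulsive behavior from before the drug is in general counted as a shift. Behavior the mMIDI already detects at Screening is a positive baseline or falls under exclusion 19. Only onset between Screening and first dose is affected.
- That a third to three quarters of Week 2 shifts are false. The 33% to 75% is calendar time. It becomes a share of new positives only under a constant onset rate, and the 75% end needs the maximum screening length.

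At the assumed rates the number involved is about 0.1 to 5 of 450 patients, the upper end only if all are screened for 6 weeks at the highest rate. No test or sample size changes.

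**What to change.** **Protocol and SAP schedule.** Add the mMIDI to Protocol 6.2.3.2, item 7, and to the Baseline cell of Protocol Table 1, Protocol Table 4 and SAP Table 1. SAP 5.7 then takes the Visit 2 value as baseline without rewording.

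**Reconcile the rules for a positive result.** Exclusion 19 and footnote j deal with positives during Screening and after Baseline. A positive at Visit 2 itself falls between them, so the sponsor must state how it is covered.

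**Patients already enrolled.** Keep all shifts in the main SAP 9.8.7 table. Label the mMIDI baseline there as the Screening value, and list days from Screening to first dose for patients first positive at Week 2. Do not move these patients to a row marked as possible predose onset. With a 1-week screening, two thirds of their interval is on drug (2/3 = 67%), and such a row could lead readers to discount a real early signal.

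**Cost.** One short interview (five gateway questions if every answer is No) at a visit where the C-SSRS is already given, so a few more minutes. An occasional positive at Visit 2 would have to be resolved before dosing and within the 6-week screening limit. The SAP change is a label and a listing and needs no new data.

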6.2.2.2 Screening / “Practice” PD Diary

Following successful completion of the PD diary training and a diary concordance session, patients/caregivers will be required to complete practice diaries on 3 consecutive pre-specified days (24-hour periods starting at 6 AM each day). The trainer/rater will telephone the patient to remind them to start keeping the practice diary prior to the start date, to review the ON and OFF definitions, and to answer any questions the patient may have regarding completion instructions.

Practice PD diaries will be returned to the diary trainer/rater and reviewed with patients/caregivers, over the telephone or in person, to assess the diaries for validity and completeness and to ensure PD diary completion instructions are fully understood

Patients with invalid practice diaries will be asked by the diary trainer/rater either to complete a second diary training and diary concordance session followed by a repeat 3-day practice diary, or else asked to repeat the 3-day practice diary, depending on the patient’s understanding of the diary completion instructions. Patients who do not satisfy concordance criteria during a second diary training and/or who return a second set of practice diaries that are invalid, will be considered screen failures.

For patients who return a valid 3-day practice diary, proceed with instructions in [Section 6.2.2.3](#).

